The purpose of this randomized, triple-blinded, prospective, feasibility study is to compare postoperative analgesia provided by PIFB when performed with local anesthetic solution with or without perineural adjuvants in patients following cardiac surgery involving sternotomy. We hypothesize that the patients receiving PIFB with bupivacaine with epinephrine, clonidine, and dexamethasone will have lower dynamic pain over the first 24 hours compared to those receiving PIFB with just bupivacaine and epinephrine. The primary outcome will be the 24 hour area under the curve (AUC) pain scores, based on patient-reported dynamic NRS pain scores with incentive spirometer (IS) use measured at 6, 12, 18, and 24 hours after block placement in patients that are extubated. We set a minimally clinical important difference (MCID) to be 10% for AUC pain scores with IS use. Secondary outcomes will include patient-reported NRS pain scores at rest at 6, 12, 18, and 24 hours after block placement; cumulative 24 hour opioid consumption; time to first postoperative opioid administration after extubation; time to extubation; duration of ICU admission; incentive spirometry volumes at 6, 12, 18, and 24 hours after block placement;

nausea incidence; vomiting incidence; postoperative delirium incidence; and patient-reported NRS satisfaction with the analgesic regimen.

Risks to Subjects

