Exclusion: Patients with any contraindications to regional anesthesia, such as history of allergy to amide local anesthetics or any of the perineural adjuvants; existing neurologic deficit in the chest wall; remaining intubated at the six hour point after block placement; weight under 50kg; undergoing emergency surgical procedures or urgent return to the operating room; active endocarditis or mediastinitis; moderate to severe right ventricular function before or after cardiopulmonary bypass; reliance on mechanical circulatory support devices, such as intra-aortic balloon pump or Impella; reliance on extracorporeal membrane oxygenation; localized or systemic infection; chronic use of high dose opioid analgesics (defined as daily use greater than 30 oral morphine milligram equivalents (OMME) for over one month prior to surgery); as well as those who are pregnant, will be excluded from participation. Intraoperative opioids will be limited to fentanyl, therefore patients who receive any other opioids will be excluded. Additionally, any administration of ketamine, methadone, and dexmedetomidine during intraoperative and postoperative settings will exclude the subjects from the study. Furthermore, postoperative administration of tramadol, NSAIDs, muscle relaxants, and Haldol will exclude the subjects from the study. Any patients who refuse enrollment or withdraw their consent will also be excluded and any of their information already collected will be destroyed.

Setting

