Subjects will be randomized on the day of surgery, specifically prior to the start of their procedure. Surgery will proceed as scheduled, and patients will be anesthetized and monitored per our usual cardiac anesthesiology practice with general anesthesia. At the end of the cardiopulmonary bypass circuit run, patients will be reassessed for the aforementioned exclusion criteria before the randomized block is placed. Patients will be blinded to their treatment arm assignment, as will all research personnel who be responsible for collection of outcome data, as well as the surgeons performing the cardiac procedure, and the critical care staff caring for the patients in the postoperative period. PIFB will be performed after skin closure and before transport from the operating room to the CVICU. For patients who are randomized at enrollment but later excluded due to exclusion criteria prior to block placement, their randomization assignment will be replaced at the end of the initial recruitment.

Interventions

Once the surgical team is finished with skin closure, bilateral PIFB will be placed by a faculty anesthesiologist well-versed in the performance of ultrasound-guided regional anesthesia and performance of PIFB blocks, or by a trained anesthesia resident or fellow directly supervised by them. This will be done by obtaining a longitudinal, parasagittal view of the costal cartilage 1-2cm lateral to the sternum at the level of the fourth or fifth rib and guiding a block needle in the cephalad direction in plane to the fascial plane between Pectus Major and Internal Intercostal muscles, with the goal of obtaining cephalad spread along the plane over multiple costal cartilage levels, as described previously²³. PIFB will be performed bilaterally using a volume of 30cc of local anesthetic solution per side, with dosing in 5cc aliquots only after confirming aspiration is negative for blood and that a small aliquot of local solution demonstrates spread in the intended plane. We will repeat aspirations in between each aliquot of 5cc of local anesthetic, as is our standard practice, to monitor for intravascular needle position.

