The time of block placement will be documented as the zero hour time point for the purposes of measurements. As described above, to collect data for the primary outcome, research staff will elicit patient-reported NRS pain scores with use of incentive spirometry at 6, 12, 18, and 24 hours post block placement. If patients are not yet extubated at the 6 hour point, they will be excluded from the study as mentioned above. Research staff will also collect data for secondary outcome measures including, but not limited to: eliciting resting NRS pain scores at 6, 12, 18, and 24 hours after block placement; measuring incentive spirometry volumes in triplicate at 6, 12, 18, and 24 hours; measuring the time after extubation to first opioid administration; time to extubation; duration of ICU admission; calculating incidence of nausea and vomiting based on the administration of the antiemetics ondansetron, metoclopramide, prochlorperazine, and promethazine; assessing delirium based on bedside ICU nurse documentation using Confusion Assessment Method in the ICU (CAM-ICU) in the first 24 hours post block placement; and measuring patient-reported NRS satisfaction with the analgesic regimen at the 24 hour point (0 represents completely unsatisfied and 10 represents completely satisfied).

For the NRS pain scores and measurement of incentive spirometer volumes at each 6, 12, 18, and 24 hours interval, there is a grace period of 1 hour. This is to give the research staff/ ICU nurse the flexibility of completing these tasks.

The cumulative 24 hour opioid consumption will be abstracted from the EMR. All opioids will be converted to oral morphine milligram equivalents (OMME) to allow for appropriate comparison using a widely available dose conversion table. These metrics will be accessed, abstracted, de-identified, and analyzed by research personnel who are blinded to group allocation.

There will also be a 30-day post-block phone call follow-up for ongoing opioid use/last use, such as frequency and dosage, and pain levels in their day-to-day activities.

Statistical Analysis

Power Analysis

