We define a minimum clinically important difference (MCID) to be a 10% reduction in area under the curve for our primary outcome. Given that no current data exist on the anticipated duration of PIFB with perineural adjuvants at our institution, we have decided to recruit 10 patients per arm for a total of 20 patients in this feasibility trial. Based on prior studies involving the use of perineural adjuvants with long-acting local anesthetics, we have noted an average duration around 20 hours for peripheral blocks performed at other sites with bupivacaine containing perineural adjuvants epinephrine, clonidine, and dexamethasone. We have therefore chosen 24 hours as the final time point, with serial checks starting at 6 hours post block placement to represent clinically important pain trajectories for patients recovering from cardiac surgery with sternotomy.

Data Analysis

Demographic information will be collected as mentioned above and compared between the groups to verify that randomization balanced important baseline variables between the control and experimental groups. For the primary outcome of AUC pain scores with use of incentive spirometry for the first 24 hours post block placement, we will compare mean and standard deviations of the overall integrated area under the curve using the trapezoid rule. For secondary outcomes with continuous variables, such as intubation or ICU duration, t-tests and confidence intervals will be calculated. For continuous variables with serial measurements, repeated measure analysis of variance (RMANOVA) will be used. Further assistance with statistical analysis is being elicited from the Clinical and Translational Science Institute (CTSI), and this IRB protocol will be updated with further details after final review with a statistician.

Missing Data Points

Missing data points for the primary outcome will be imputed by a mixed effects modeling framework that allows us to use all available data points to tests hypotheses about differences between the two groups at each time point. Models will be implanted using the 'lme4' package in R statistical software.

Human Subjects Protection

Subject Recruitment Methods

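### Patients still intubated at 6 h are excluded after the block, so time to extubation is cut off at about 6 h; the postoperative drug exclusions also condition the other comparisons on post-treatment events

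*Combined protocol and SAP*

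**What the plan says.** - **Sequence.** Patients are randomised on the day of surgery, before the procedure (Randomization). The block follows skin closure, and patients go to the ICU still intubated (Interventions). Block placement is time zero (Measurements).
- **6 h rule.** The exclusion list in Selection Criteria includes "remaining intubated at the six hour point after block placement". Measurements repeats it: "If patients are not yet extubated at the 6 hour point, they will be excluded from the study as mentioned above".
- **Drug rule.** Selection Criteria adds that "any administration of ketamine, methadone, and dexmedetomidine during intraoperative and postoperative settings will exclude the subjects from the study" and that "postoperative administration of tramadol, NSAIDs, muscle relaxants, and Haldol will exclude the subjects from the study". Neither sentence has a time limit, although the scheduled bedside assessments end at 24 h.
- **Replacement.** Randomization provides only for patients "later excluded due to exclusion criteria prior to block placement, their randomization assignment will be replaced at the end of the initial recruitment". Nothing is said about patients excluded after the block.
- **Outcomes and tests.** The secondary outcomes in Objectives include "time to first postoperative opioid administration after extubation; time to extubation; duration of ICU admission". Data Analysis states: "For secondary outcomes with continuous variables, such as intubation or ICU duration, t-tests and confidence intervals will be calculated".
- **Missing data.** For the primary outcome, Missing Data Points plans a mixed model that "allows us to use all available data points". It does not mention excluded patients, and no analysis set is defined.

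**The concern.** The 6 h rule is written as an eligibility criterion but can only be applied after treatment. It selects on the same event that one secondary outcome measures. The rationale section names earlier extubation among the benefits of an ideal block, so the excluding event is one the treatment is hoped to change. If the adjuvants do shorten intubation, the slow end of the control arm is removed more often and the measured benefit shrinks.

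The drug rule also acts after treatment. The documents do not say why the listed drugs would be given. If some are given for pain or delirium, the patients with most pain or delirium leave the analysis, and the pain, opioid, ICU-stay, delirium and satisfaction comparisons are made on a selected remainder.

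With 10 patients per arm, each unreplaced exclusion is 10% of an arm, in a trial meant to show feasibility.

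**Working it through.** **Step 1: the bound, from the text alone.** The time origin is the block, all patients are intubated then, and anyone still intubated at 6 h leaves the study. The longest extubation time that can be analysed is therefore 6 h. The 1 h grace period is given only for pain scores and spirometry volumes; stretched to extubation, it would move the bound to 7 h.

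**Step 2: size for time to extubation.** There is no figure in the plan to reproduce, so all inputs here are assumptions. Take a lognormal time with median m and log-SD s:

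- full mean = m·exp(s²/2)
- fraction kept p = Φ((ln 6 − ln m)/s)
- kept mean = full mean × Φ((ln 6 − ln m − s²)/s) / p

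Worked case, medians 5 h (control) and 4 h (experimental), s = 0.5:

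- Control: full mean 5.67 h, p = 0.642, kept mean 3.94 h.
- Experimental: full mean 4.53 h, p = 0.791, kept mean 3.56 h.
- Difference: 1.13 h in full, 0.37 h kept.

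The last column is the standard error at 10 per arm before truncation, √((SD₁² + SD₂²)/10), with SD = full mean × √(exp(s²) − 1).

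| Medians (h), s | Excluded, control v experimental | True difference (h) | Kept difference (h) | Lost | SE (h) |
|---|---|---|---|---|---|
| 3.5 v 3, 0.3 | 3.6% v 1.0% | 0.52 | 0.44 | 15% | 0.47 |
| 4 v 3.5, 0.3 | 8.8% v 3.6% | 0.52 | 0.37 | 29% | 0.54 |
| 5 v 4, 0.5 | 35.8% v 20.9% | 1.13 | 0.37 | 67% | 1.22 |
| 6 v 5, 0.4 | 50.0% v 32.4% | 1.08 | 0.29 | 73% | 1.11 |

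With a 7 h cut the loss in these rows runs from 6% to 63%. More controls than experimental patients are lost in every row.

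**Step 3: size for pain under the drug rule.** Assume mean NRS 5 v 4, SD 1.8, and a logistic probability of exclusion that rises between NRS 3 and NRS 7. The last column repeats the calculation for 5 v 4.5, a true effect exactly at the plan's 10% MCID.

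| Exclusion at NRS 3 to NRS 7 | True 1.00 point (20.0%) reads | True 10.0% reads |
|---|---|---|
| 5% to 50% | 0.84 (18.5%) | 9.1% |
| 2% to 30% | 0.89 (18.8%) | 9.3% |
| 2% to 10% | 0.98 (19.8%) | 9.9% |
| flat 10% | 1.00 (20.0%) | 10.0% |

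The standard error at 10 per arm is 1.8 × √(2/10) = 0.80 points. With no treatment effect the difference stays at zero in all four patterns.

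A steeper dependence costs more. With an AUC coefficient of variation of 30% and logistic slopes of 5 to 10 per unit of relative AUC, 14% to 33% of controls and 10% to 24% of experimental patients are excluded. A true difference of 10% of the control mean then falls to between 8.7% and 6.3% of that mean. The standard error there is 30% × √(2/10) = 13.4%.

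**Step 4: delirium.** If a share h of delirium cases receives a listed drug, the recorded rate is p(1 − h)/(1 − ph). Assume true rates of 20% v 10%.

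- h = 0.25: 15.8% v 7.7%, a difference of 8.1 points.
- h = 0.50: 11.1% v 5.3%, a difference of 5.8 points.

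The ratio stays near 2:1, while the difference falls from 10.0 points.

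**The case against.** - **Dynamic pain cannot be scored in an intubated patient, and Objectives limits the primary outcome to extubated patients.** This stands as a reason for a missing 6 h score. It is no reason to drop the later scores, the extubation time, ICU stay or delirium assessments.
- **The practical effect is small in a 20-patient feasibility trial.** In every row of Step 2 the lost difference (0.08, 0.15, 0.76 and 0.79 h) is below one standard error, and attenuation is towards no effect. The severe rows assume that 36% to 50% of controls are still intubated at 6 h, which may not fit a design that starts pain checks then. This lowers the stakes. It does not make a truncated outcome interpretable, and the trial does state a comparative hypothesis and tests.
- **The part about the listed drugs rests on assumptions.** This stands. Neither the reasons for use nor any delirium rate is in the documents. Step 3 models drug use only; the effect of the 6 h rule on pain, opioid use and ICU stay is not quantified.
- **Data Analysis says more detail will follow after statistical review.** That softens the complaint about the missing analysis set. It does not undo the exclusions, and bedside scores not collected from a dropped patient cannot be recovered later.
- **Treating the 6 h score as a missing visit assumes missingness at random.** True, but the planned mixed model already makes that assumption. It should be stated.

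**Conclusion.** The concern holds. That time to extubation is truncated at about 6 h follows from the text alone, so this secondary outcome is wrong as written. How much is lost depends on how often patients remain intubated at 6 h: from slight (15%) to severe (73%) over the assumed lognormal cases.

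For the other outcomes the rules condition the comparison on post-treatment events, and correcting this is a cheap improvement. The bias in pain is nil if treatment has no effect or if exclusion is unrelated to pain. Otherwise it is small beside the sampling error at 10 per arm. Confidence is high for the first part and lower for the second, where every input is assumed. This should be fixed before follow-up is stopped on any blocked patient.

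**What to change.** 1. Limit exclusion criteria to conditions that can be assessed before the block.
2. Define the main analysis set as all randomised patients who received the block, in their assigned arm.
3. Leave the drug restrictions unchanged. Record a listed drug, with its time, as a protocol deviation or intercurrent event, and keep the patient's data.
4. Treat a 6 h score that cannot be obtained because of intubation as a missing visit in the planned mixed model, state the missing-at-random assumption, and keep the later scores.
5. Report time to extubation, ICU stay, delirium and opioid use in all blocked patients. A rank-based or time-to-event comparison would suit extubation times once the long ones are kept.
6. Keep the analysis with the current exclusions as a sensitivity analysis.
7. Report post-block events by arm and reason as a feasibility result.

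The cost is an amendment of wording, with no extra patients and no new type of assessment. Staff would continue the scheduled assessments to 24 h and the 30-day call for patients who are now dropped. Some analysed patients will have had non-protocol analgesics, which the sensitivity analysis addresses.

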Patients randomized to the control arm will receive bilateral PIFB with a total of 60cc of 0.25% bupivacaine with 2.5mcg/cc epinephrine (1:400,000 dilution), and those in the experimental arm will receive bilateral PIFB with a total of 60cc of 0.25% bupivacaine with 2.5mcg/cc epinephrine (1:400,000 dilution), 1.67mcg/cc clonidine, and 0.1mg/cc preservative-free dexamethasone.

Patients will be monitored throughout block placement using standard ASA monitors including telemetry, heart rate, blood pressure, pulse oximetry, and end-tidal capnography. Following placement of bilateral PIFB, patients will be transported still intubated to the ICU with propofol infusion for sedation, as per institutional protocol for routine postoperative care.

As is our current practice, patients will be managed with ICU nursing-administered titrated boluses of IV fentanyl for analgesia before extubation based upon signs of nociception, including hypertension, tachypnea, facial grimace, and motor agitation. Patients will have as-needed doses of oxycodone and/or hydromorphone ordered for analgesia after extubation, unless they have a contraindication or allergy, in which case a suitable alternative at equianalgesic doses will be ordered.

Materials

Ultrasound guidance for imaging the relevant anatomy will be obtained using a linear ultrasound probe. All PIFB will be performed in a sterile manner, using sterile gloves, sterile ultrasound probe cover, sterile short-bevel block needle, and skin cleaning using an aseptic cleaning solution prior to placement. All products used are FDA-approved for the above-mentioned procedures, and an Investigational New Drug (IND) exemption has been obtained for use of the study medications used in this protocol under FDA IND165506.

Measurements

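### Nausea incidence and vomiting incidence are named as two outcomes but rest on one antiemetic-use measure that can neither separate the symptoms nor pick out symptom-triggered doses

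*Combined protocol and SAP*

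**What the plan says.** The Objectives section lists the secondary outcomes separated by semicolons. Three consecutive entries read "nausea incidence; vomiting incidence; postoperative delirium incidence", so nausea and vomiting are separate outcomes there.

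The Measurements section describes how each secondary outcome is obtained. For these two it has one entry: "calculating incidence of nausea and vomiting based on the administration of the antiemetics ondansetron, metoclopramide, prochlorperazine, and promethazine". No patient question, nausea score, emesis count or nursing record is named for either symptom.

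The same sentence goes on to delirium, and the phrase "in the first 24 hours post block placement" is attached to that item. It is not clear that it also governs the antiemetic item. Measurements does set block placement as time zero, and the Randomization section places the block after skin closure.

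Nothing limits the counted antiemetic doses to those given for symptoms. The protocol does draw that kind of distinction for opioids, in the Interventions section: "Patients will have as-needed doses of oxycodone and/or hydromorphone ordered for analgesia after extubation".

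On analysis, the Data Analysis section says: "For secondary outcomes with continuous variables, such as intubation or ICU duration, t-tests and confidence intervals will be calculated". It adds a repeated-measures method for serial continuous variables and names no method for yes/no outcomes.

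**The concern.** Two differently named outcomes appear to be filled from one variable. If the rule is applied as a simple indicator of whether any of the four drugs was given, every patient has the same value for nausea as for vomiting. The two incidences and their between-arm differences then coincide, and neither is a count of the symptom it is named after.

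The error can go both ways. Vomiting is overstated when a patient was treated for nausea alone. Both symptoms are understated when an episode went untreated. If scheduled or prophylactic doses fall inside the counting period, they are counted as events as well.

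The outcome has some weight in the trial's rationale: the Summary/Purpose/Rationale section cites less postoperative nausea and vomiting as a demonstrated benefit of this block. A feasibility trial is also the place to find out whether an outcome can be measured as named before a larger study relies on it.

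**Working it through.** The protocol gives no rate, event count or power for nausea or vomiting, so there is no figure of its own to reproduce. The main check is logical. The figures after it are illustrations on assumed rates.

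**1. The two sections side by side.** Objectives: two outcomes. Measurements: one source, administration of any of four drugs. Let A = 1 if a patient receives any of them, otherwise 0. With nothing else recorded, nausea = A and vomiting = A. Then:

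- Nausea only, treated: A = 1, so vomiting is recorded although none occurred.
- Nausea or vomiting, untreated: A = 0, so neither is recorded although one occurred.
- No symptom, scheduled dose in the window: A = 1, so both are recorded although neither occurred.

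The first two errors need no assumption about prophylaxis. The third arises only if such doses are given.

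**2. Size of the vomiting overstatement (assumed rates).** Suppose 40% of patients receive an antiemetic and a share s of them vomited. Treated vomiting is 0.40 × s:

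- s = 0.25: 0.40 × 0.25 = 10%
- s = 0.50: 0.40 × 0.50 = 20%
- s = 0.75: 0.40 × 0.75 = 30%

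The rule reports 40% in each case. In an arm of 10, that is 4 recorded vomiting events, of which between 1 (4 × 0.25) and 3 (4 × 0.75) are real.

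**3. Dilution if non-symptom doses are counted (conditional).** Let p be the rate of symptom-triggered antiemetic use. Let q be the share of patients given a scheduled or prophylactic dose in the window, independent of symptoms and equal in both arms. The measured rate is 1 − (1 − p)(1 − q). Take p = 40% in control and 20% in experimental, with 10 per arm and a two-sided 5% comparison of proportions (normal approximation):

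| q | Control | Experimental | Difference | Approximate power |
|---|---|---|---|---|
| 0 | 40% | 20% | 20 points | 16% |
| 0.25 | 55% | 40% | 15 points | 10% |
| 0.50 | 70% | 60% | 10 points | 7% |
| 0.75 | 85% | 80% | 5 points | 5% |
| 1 | 100% | 100% | 0 points | not computed |

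For example, at q = 0.50 control is 1 − 0.60 × 0.50 = 0.70 and experimental is 1 − 0.80 × 0.50 = 0.60. The difference is always the true difference times (1 − q). With 60% against 30%, it falls from 30 points to 22.5, 15, 7.5 and 0.

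The first row matters as much as the others: with no dilution at all, power is only about 16%.

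**The case against.** The strongest reply is that Measurements describes one combined outcome, nausea and vomiting together, as the Rationale does when it uses the single term for postoperative nausea and vomiting. The rule also says only that incidence is based on administration; it does not say that any one dose is an event for both symptoms. That reading is possible, and on it there are no duplicate results. It still contradicts Objectives, so the two sections need reconciling, and the combined variable would still be drug use labelled as symptom incidence.

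A reader might infer that prophylactic doses are in fact being counted and are pushing both arms towards 100%. The documents do not support that. Antiemetic prophylaxis is mentioned nowhere, and time zero is block placement after skin closure, so doses given earlier in the operation fall before it. What can be said is that the rule does not exclude such doses after the block.

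A reader might also infer that the rule would hide a real treatment effect, or yield two matching p-values that pass for independent evidence. Neither holds firmly. The Power Analysis section states "we have decided to recruit 10 patients per arm for a total of 20 patients in this feasibility trial", and at that size a 20-point difference would usually be missed even with perfect measurement. No test is named for yes/no outcomes, so no p-value is promised.

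Antiemetic use is an objective proxy, and blinding of critical care staff and outcome collectors limits bias between arms. That stands, but it does not make the proxy a measure of either symptom. The protocol calls its list of secondary measures non-exhaustive and says its statistical details will be updated, but it names no other source for these symptoms, and a later analysis plan cannot recover what was not recorded at the bedside.

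**Conclusion.** The point holds as an outcome-definition error. Two named secondary outcomes share one proxy that cannot tell them apart, misses untreated episodes and records vomiting in patients treated for nausea alone. This follows from the text without outside facts and goes beyond missing detail, because following the stated rule misclassifies patients. The open window and the silence on dose type are additional gaps.

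The size cannot be fixed from the documents. The range of 10% to 30% treated vomiting reported as 40% rests on assumed rates. The dilution table rests further on non-symptom doses being given after the block, independently of symptoms and equally in both arms.

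The reach is limited: the primary outcome and the sample size are untouched. The change is worth making before data collection, but it does not threaten the trial's main result.

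**What to change.** **Preferred.** At the 6, 12, 18 and 24 h visits that research staff already make, add two yes/no items: any nausea, and any vomiting. The recall period at 6 h should be since extubation, because patients reach the ICU intubated and sedated; at later visits it should be since the previous visit. Derive each incidence from its own item, as at least one yes by the 24 h visit, and state that the period at risk starts at extubation.

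Report antiemetic use as a separate outcome named *symptom-triggered antiemetic given, 0–24 h after block*, restricted to the four listed drugs and leaving out scheduled or prophylactic doses. The protocol should say how dose type is identified, for example from the order in the medical record, if that shows it.

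**Fallback.** If the questions are not added, delete nausea incidence and vomiting incidence from Objectives and Measurements and put that single antiemetic-use outcome in their place. This needs no new bedside collection and removes the conflict between the sections.

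**Cost.** Two fields on an existing form and a few lines of text. Bedside visits become slightly longer, and some recall error must be expected in patients who are still sedated or delirious. Treatment, sample size and the primary outcome do not change.

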Patients between 18 and 90 years of age, scheduled to undergo cardiac surgery involving sternotomy at Atrium Health Wake Forest Baptist will be screened for eligibility. These patients will be approached for enrollment by research staff either during their preoperative assessment clinic visit prior to their surgery date, or when admitted as inpatients and scheduled for surgery. During this visit, the study will be discussed in detail, and eligible participants will be offered the ability to ask any questions and sign consent forms at that time, or decide at a later time prior to surgery. Study staff will also review the surgical schedule and offer to call eligible participants to discuss the research study to determine their interest. At that time, if interest is shown, the consent will be emailed to them for review prior to their hospital admission to allow adequate time for consideration. Those subjects will then be seen on the morning of surgery to obtain a written informed consent. All patients will be provided with a signed copy of their written informed consent for their records.

Study Protocol

Baseline data collection

After time of consent, enrolled patients will be informed on the appropriate use of an incentive spirometer (IS), asked to rate their baseline verbal pain score both at rest and with use of an incentive spirometer (IS) on the eleven-point numerical rating scale (NRS: 0-10, where 0 represents no pain and 10 represents the worst imaginable pain). Maximum effort IS volumes will be measured in triplicate and averaged, and patient characteristics will be recorded, including age, gender, height, weight, BMI, ASA physical status classification score, surgeon, planned surgical procedure, as well as preoperative opioid use and doses.

Randomization

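### The plan uses baseline data only in a 10 v 10 balance check that cannot verify balance, and leaves the collected baseline dynamic pain and preoperative opioid dose out of the AUC and 24 h opioid analyses

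*Combined protocol and SAP*

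**What the plan says.** Under Baseline data collection, patients rate pain on the 0-10 NRS at rest and with the incentive spirometer, and the recorded characteristics run from age to planned procedure, "as well as preoperative opioid use and doses". The exclusion criteria remove chronic high-dose opioid users, defined by "daily use greater than 30 oral morphine milligram equivalents (OMME) for over one month prior to surgery". Lower or shorter use therefore stays eligible.

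The Power Analysis section sets the size: "we have decided to recruit 10 patients per arm for a total of 20 patients in this feasibility trial". The Data Analysis section gives baseline data one use. They are to be "compared between the groups to verify that randomization balanced important baseline variables between the control and experimental groups". It names no test, no threshold and no consequence if imbalance is found. For the primary outcome, "we will compare mean and standard deviations of the overall integrated area under the curve using the trapezoid rule". Continuous secondary outcomes get t-tests and confidence intervals, and serial measures get repeated-measures ANOVA. The 24 h opioid total is not named individually, so the t-test rule covers it by default. No baseline covariate is named in any analysis, including the mixed model for missing primary-outcome data. The Randomization section describes no stratification.

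**The concern.** A comparison of 10 with 10 has too little information to show that the arms are balanced. A reassuring result would be read as verification when it shows little, and a worrying one has no stated consequence. If adjustment were chosen only after an imbalance had been seen, it would be data-driven.

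Two obvious candidate covariates are already recorded. Baseline NRS with spirometer use is the same scale and manoeuvre as the primary outcome, measured before treatment. Preoperative opioid dose is the natural covariate for postoperative opioid consumption. With neither in the model, whatever imbalance arises stays in the estimate in proportion to how strongly the covariate predicts the outcome.

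**Working it through.** **The plan's own figure.** Ten per arm is given without alpha, power, SD or control mean, so it cannot be reproduced. For orientation, at an assumed two-sided 5% level, 10 per arm gives 80% power for the stated 10% difference only if the coefficient of variation (CV) of the AUC is 0.10 × √5 / (1.960 + 0.842) = 0.08.

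**1. How often chance imbalance arises.** The SE of a standardised baseline difference is √(2/10) = 0.447 SD.
- P(gap above 0.5 SD) = 2 × [1 − Φ(0.5/0.447)] = 0.264.
- P(gap above 0.75 SD) = 0.094.

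**2. What a comparison could detect.** The plan names no test. If it were a 5% t-test (18 df), the observed gap would need to reach about 2.101 × 0.447 = 0.94 SD to be flagged. By simulation, about 81% of gaps of 0.5 SD or more would go unflagged.

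**3. Effect on the unadjusted AUC difference.** Shift in outcome SD = r × imbalance, where r is the correlation between baseline and outcome. As a percentage of the control mean, multiply by the CV. The documents give neither r nor CV, so both are assumptions.

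| r | shift at 0.5 SD imbalance | % of control mean, CV 0.3 to 0.5 |
|---|---|---|
| 0.1 | 0.05 SD | 1.5 to 2.5 |
| 0.3 | 0.15 SD | 4.5 to 7.5 |
| 0.5 | 0.25 SD | 7.5 to 12.5 |

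The plan's minimum important difference is 10%.

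**4. What adjustment does.** In 200,000 simulated trials per value of r (normal data, 10 per arm), type I error over all randomisations was about 5% with or without adjustment. In the roughly 21% of trials with an imbalance of at least 0.5 SD that a 5% test would not flag, the results were:

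| r | mean shift, unadjusted | type I error, unadjusted |
|---|---|---|
| 0.1 | 0.07 SD | 5.2% |
| 0.3 | 0.20 SD | 6.1% |
| 0.5 | 0.33 SD | 7.8% |
| 0.7 | 0.46 SD | 9.5% |

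With ANCOVA the mean shift was about 0 and the error about 5% throughout.

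**5. Precision.** The variance ratio of ANCOVA to unadjusted is (1 − r²) × (1 + 1/(20 − 4)) = (1 − r²) × 17/16.
- r = 0: 1.0625, so the SE is √1.0625 = 1.03 times as large.
- r = 0.3: 0.967. r = 0.5: 0.797.
- Break-even: r² = 1/17, so r = 0.24.

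**6. Opioid illustration.** Assume two or three of the 20 patients take 30 OMME a day, continue it through the 24 h window, and the rest take none.
- Three users, all in one arm: probability 2 × C(10,3)/C(20,3) = 240/1140 = 21%. The arm difference shifts by 3 × 30/10 = 9 OMME.
- Two users, both in one arm: probability 2 × C(10,2)/C(20,2) = 90/190 = 47%. The shift is 2 × 30/10 = 6 OMME.

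The cost of adjusting in those splits is larger than the average 3%. The variance multiplier of the treatment estimate is 2/10 + d²/Sxx, where d is the difference in covariate means and Sxx the within-arm sum of squares.
- 3-0 split: Sxx = 3 × 900 − 10 × 81 = 1890. Multiplier 0.200 + 81/1890 = 0.243, and √(0.243/0.200) = 1.10.
- 2-0 split: Sxx = 2 × 900 − 10 × 36 = 1440. Multiplier 0.200 + 36/1440 = 0.225, and √(0.225/0.200) = 1.06.

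The SE is thus about 6% to 10% wider before any reduction in residual variance.

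**The case against.** Several points on the other side stand.

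- A reader might infer that the unadjusted analysis is biased or invalid. It is not. Randomisation makes it unbiased on average, and its interval already allows for chance imbalance. The loss is conditional on the imbalance that occurs.
- A reader might also infer that habitual opioid use will be counted as postoperative need. The documents do not establish this. The Interventions section describes fentanyl boluses before extubation and as-needed oxycodone or hydromorphone after it, and nothing describes continuing home opioids. Carry-over, the number of users and their dose are all assumptions, and no SD or expected total is given against which to judge 6 or 9 OMME.
- The plan does not say that it will run significance tests at baseline. It says only that variables will be compared. The sentence opens with demographic information and reaches pain and opioid dose only by referring back to the baseline list.
- Baseline pain is scored before sternotomy and may be near 0 in most patients, in which case adjusting for it gains little or nothing. With few opioid users, the slope in the opioid model would rest on two or three people.
- This is a 20-patient feasibility trial, and the section says it will be updated after review with a statistician.

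These points limit the weight of the concern. They do not remove it, because the promised update commits to no covariate and a 10 v 10 comparison still cannot verify balance.

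**Conclusion.** The point holds as a cheap improvement, not as a flaw that invalidates the analysis. Two parts are firm. The balance check cannot do what it is meant to do and leads to no action. Two relevant baseline measurements are collected and then left out of the analyses they bear on.

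The size is uncertain. At a 0.5 SD imbalance, the shift in the AUC difference ranges from 1.5% of the control mean (r = 0.1, CV 0.3) to 12.5% (r = 0.5, CV 0.5). Precision improves only if r exceeds about 0.24. These figures rest on assumed correlations, CVs and normal data. The opioid example rests further on assumed carry-over. That the 24 h opioid total gets a t-test is inferred from the general rule.

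**What to change.** Before unblinding, add to the Data Analysis section:

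1. The primary AUC is analysed by ANCOVA with baseline NRS during spirometer use as the only covariate.
2. The 24 h OMME total is analysed by ANCOVA with preoperative daily OMME as the only covariate. Fix the outcome scale (raw, log or rank) now, not after looking at skewness.
3. Unadjusted results are reported beside both.
4. The wording about verifying balance is replaced by a descriptive baseline table without tests.

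The cost is wording, since both covariates are already collected and no patient procedure changes. Each model spends one degree of freedom. The SE is about 3% wider if the covariate is unrelated. In the opioid model it may be about 6% to 10% wider, before any residual-variance gain, if the only two or three users fall in one arm. If nearly all baseline pain scores are 0, the first model gains little or nothing.
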